### Research objectives:

1. To conduct a comparative assessment of the dynamics of nutritional deficiency and nutritional status of patients operated on for malignant tumors of the hepatopancreatoduodenal zone in the early postoperative period during isolated enteral, isolated parenteral and mixed types of nutritional support.
2. To analyze the dynamics of the state of protein and carbohydrate metabolism, the consistency of liver function in cancer patients operated on for malignant tumors of the hepatopancreatoduodenal zone, against the background of isolated enteral, isolated parenteral and mixed type of nutritional support in the early postoperative period.
3. To determine the degree of effectiveness of these methods of nutritional support in this category of patients based on the totality of the results of assessing nutritional status and the dynamics of the level of basal metabolism in these patients in the early postoperative period.

Researched 91 patients, will be divided into 3 groups:

1. The first group (n=31) included patients who received enteral nutrition (EN) after surgery.
2. The second group (n=30) included patients receiving parenteral nutrition (PN).
3. The third group (n=30) receiving mixed nutrition (MN), as is commonly considered the method of partial parenteral nutrition, in the early postoperative period.

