## **Methods of statistical data analysis**

All patients hospitalized for special treatment with a verified diagnosis of a malignant neoplasm were subjected to the study in the abdominal department of the KGP at the Regional Oncological Dispensary, Karaganda.

The quantitative and qualitative indicators obtained during the study were analyzed using descriptive and analytical statistics methods. For statistical processing of qualitative (diagnosis codes, dichotomous data) and quantitative variables: symptom intensity, severity, frequency of occurrence, we used the calculation of the median level (Me) with 25%-75% quartiles (Q25; Q75) and the calculation of the arithmetic mean (M) with error (m) and 95% confidence interval (95% CI), standard deviation (s). Quantitative variables were checked for normality of distribution using the Kolmogorov-Smirnov test, as well as the module of Skewness and Kurtosis for quantitative variables  $| \leq 2 |$ . Differences in the 3 groups of patients for quantitative variables corresponding to a normal distribution were identified using the Student's t test for unrelated groups, first for 3 or more groups, and then in pairs for each pair using the Student's t test. Differences for rank variables, or quantitative but not normally distributed for unrelated groups, were determined by the Kruskal-Wallis test or median test for 3 groups, and then pairwise or non-parametric Mann-Whitney test for each of the 3 pairs (groups 1 and 2, groups 1 and 3, groups 2 and 3), and for related groups (dynamic observations) by the Kendall test for 3 groups and then by the Wilcoxon test (Wilcoxon) for each of the 3 pairs (baseline, after 5 days and after 10 days).

Correlation was performed for quantitative variables according to Pearson and for rank variables according to Spearman. Statistical processing of the results was carried out using the Statistica program version 10.

**Results and discussion.** The nutritional status of patients in all three groups before surgery and during the 10-12 days of the postoperative period according to the methods of assessing nutritional status NRS, SGA and NRI was assessed as normal, moderate and severe malnutrition

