As can be seen from the presented data, in the preoperative period, according to the SGA assessment, 24 patients in the enteral group, 19 patients in the parenteral group, and 17 patients in the mixed group had normal nutritional status before surgery, with variations relative to patients with moderate to severe malnutrition. Assessment of nutritional status before surgery using the NRI scale allowed us to confirm the nutritional status of the vast majority of patients in all groups as relatively normal

Thus, in 62 of the 91 patients examined, the NRI was assessed as true negative (normal nutritional status), in 26 as true positive (moderate malnutrition), and in 3 as severe malnutrition. Data from the NRI method during this time period had a strong correlation with the results of the SGA scale ( $p < 0.005$ ).

On the 10-12th day of the postoperative period in patients of the “enteral” group, the results of the assessment on the SGA scale remained unchanged; according to the NRI rating scale, there was an increase in “moderate malnutrition” per patient (25%).

With parenteral nutritional support, 17 patients had “normal nutrition”, 14 patients had moderate malnutrition, with regression of “severe malnutrition” in 1 patient. In the mixed nutrition group, there was a complete elimination of signs of “severe malnutrition” by 100% according to the given scales ( $p < 0.005$ ).

In patients of all study groups, throughout the entire period of nutritional support, fluctuations in the level of basal metabolism were observed in average values of  $335.89 \pm 53.6$  kcal/day (13.44%) from the initial value - 1-2 days of the postoperative period and were due to variability body mass index and the dynamics of the temperature curve after surgery.

In patients in the groups with enteral and parenteral nutrition, by the end of these types of energy subsidies (days 10-15), the level of basal metabolism was observed to approach its initial values -  $2500.1 \pm 353.4$  kcal/day and  $2350.0 \pm 330.5$  kcal/day days accordingly. With a mixed type of nutrition, there was a statistically significant decrease in the level of basal metabolism by 6.78% ( $2250.0 \pm 105.2$  kcal/s), which allows us to conclude that patients' energy costs are more effectively covered with this option of nutritional support in a comparative aspect with isolated types nutrition ( $p < 0.03$ ).

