### **Conclusion:**

1. According to the NRI nutritional status assessment scales, the SGA mixed type of nutritional support at the time of transfer of patients to the specialized department and upon completion of this area of intensive therapy in the specialized department by 12-15 days of the postoperative period showed higher effectiveness in stabilizing the condition and maintaining the patients' caloric intake in a comparative aspect with the group of isolated enteral nutrition and parenteral nutrition.
2. Throughout the entire period of isolated enteral, parenteral and mixed nutritional support, all patients (100%) showed a relatively constant level of total blood protein.
3. In patients of all three groups, throughout the entire period of nutritional support, fluctuations in the level of basal metabolism were observed, which was due to the variability of body mass index and the dynamics of the temperature curve after surgery. In patients in the groups with enteral and parenteral nutrition, by the end of nutritional support (days 15-20), the level of basal metabolism was observed to approach its initial values. With a mixed type of nutrition, a statistically significant decrease in the level of basal metabolic rate was observed, which suggests a more effective coverage of the energy costs of patients with this option of replenishing nutritional ingredients.

**Researcher:** [name], PhD student KSMU

[contact].

e-mail: [contact].

[figure not shown]
Signature  17.03.2020

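### One unlabelled p<0.03 is used to rank mixed feeding above both isolated routes on basal metabolism, but the printed figures do not support the ranking over parenteral feeding

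*Combined protocol and SAP*

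**What the plan says.** The Report's Results and discussion (under Methods of statistical data analysis) gives basal metabolism by arm. For the enteral and parenteral arms, "by the end of these types of energy subsidies (days 10-15), the level of basal metabolism was observed to approach its initial values", followed by 2500.1 ± 353.4 and 2350.0 ± 330.5 kcal/day. For mixed feeding, "there was a statistically significant decrease in the level of basal metabolism by 6.78" per cent, to 2250.0 ± 105.2. The same sentence infers that energy costs are "more effectively covered with this option of nutritional support in a comparative aspect with isolated types nutrition" and ends with p<0.03. None of the ± figures is labelled.

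Conclusion item 3 repeats the contrast between the two isolated groups and the mixed group. It says that the decrease with mixed feeding "suggests a more effective coverage of the energy costs of patients with this option of replenishing nutritional ingredients", and gives no p-value.

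For normally distributed variables, the methods section prescribes a comparison of the three groups "and then in pairs for each pair using the Student's t test". For other variables it prescribes Kruskal-Wallis or the median test, then Mann-Whitney for each of the three pairs. The text on basal metabolism reports no pairwise result.

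**The concern.** The isolated types are two arms, so the sentence makes two claims: mixed better than enteral, and mixed better than parenteral. One p-value is offered for both. The gap in printed means is two and a half times larger against enteral than against parenteral, so the two claims need not stand or fall together.

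Research objective 3 names the dynamics of basal metabolism as a basis for judging the feeding methods, and this result supplies one of the three conclusions. A reader would take it that mixed feeding beat parenteral feeding at p<0.03.

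**Working it through.** **Inputs.** Means and ± as quoted from Results and discussion. The mixed figure is printed in kcal/s and taken as kcal/day. Group sizes of 31, 30 and 30 come from the Report's Research objectives. Assumptions for steps 1 to 3: all three means are end-of-support values, and ± is the SD except where step 2 varies it.

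**1. Pairwise contrasts of end levels (Welch).** SE = √(s₁²/n₁ + s₂²/n₂).

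- Mixed minus enteral: 2250.0 - 2500.1 = -250.1. SE = √(353.4²/31 + 105.2²/30) = 66.3, t = -3.77, p = 0.0006 (Student 0.0004), 95% CI -385 to -116.
- Mixed minus parenteral: 2250.0 - 2350.0 = -100.0. SE = √(330.5²/30 + 105.2²/30) = 63.3, t = -1.58, p = 0.123 (Student 0.120), 95% CI -229 to 29.

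With this SE, p = 0.03 needs a difference of about 2.225 × 63.3 = 141 kcal/day. The printed difference is 100.

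**2. Other readings of ±, mixed against parenteral.**

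| Reading | p |
|---|---|
| Mixed ± is a standard error, parenteral ± an SD | 0.41 |
| Every ± is a standard error | 0.77 |
| Every ± is a 95% CI half-width | 0.56 |
| Both SDs, but mixed SD about 340 like the other arms | 0.25 |

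If every ± is a standard error, the enteral contrast fails too (p about 0.50), and the SDs would be 353.4√31 = 1968, 330.5√30 = 1810 and 105.2√30 = 576 kcal/day. SD is the more plausible reading and the kinder one to the Report.

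**3. Tests on the same figures that do meet p<0.03.**

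- Three-group test (one-way ANOVA): overall mean 215,503.1/91 = 2368.2; between-group mean square about 968,400/2 = 484,200; within-group mean square 286.74² = 82,220; F = 5.89, p = 0.004.
- Enteral and parenteral pooled against mixed: p = 0.008 (Welch 0.0005).
- Mixed arm's own fall: implied baseline 2250.0/(1 - 0.0678) = 2413.6, a fall of 163.6. The baseline SD is not given. At an assumed 353.4 with zero within-patient correlation, t = 2.43 and p = 0.021. A smaller SD or a positive correlation makes p smaller.

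**4. A comparison of changes.** Suppose the parenteral arm returned exactly to baseline and the mixed arm fell by 163.6. With the printed SD at both times, the SD of change is s√(2(1 - r)), where r is the within-patient correlation. At r = 0.4 this gives 362.0 and 115.2, SE = √((362.0² + 115.2²)/30) = 69.4, t = 2.36, p = 0.022 (Welch 0.024). At r = 0.3, p = 0.033; at r = 0.7, p = 0.0015. If the mixed SD were 330.5, p would be 0.085 at r = 0.4 and 0.016 at r = 0.7. The documents give neither r nor the parenteral change.

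**5. Initial or final means?** The preceding paragraph equates 335.89 kcal/day with 13.44% of the initial value: 335.89/0.1344 = 2499, very close to the enteral 2500.1. This is a hint only. That paragraph covers all groups, and averaging 2500.1, 2350.0 and the implied mixed baseline gives (31 × 2500.1 + 30 × 2350.0 + 30 × 2413.6)/91 = 2422, not 2499.

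**6. Spread.** 105.2/353.4 = 0.30 and 105.2/330.5 = 0.32. The variance ratios are 11.3 and 9.9.

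**The case against.** The strongest reply is that the Report argues from change, not from end levels: the isolated arms drift back towards baseline while the mixed arm falls. Step 4 shows that a contrast of changes against parenteral could reach p<0.03 at a moderate correlation. A fairly high one is plausible, because basal metabolism was calculated by Harris-Benedict from sex, age, height and weight, of which only weight moves much in two weeks. This stands. It shows that the claim might be supportable, not that it has been supported: no change is printed for the parenteral arm and no such contrast is reported.

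A second reply is that 2500.1 and 2350.0 may be initial values, in which case -100 compares a parenteral baseline with a mixed end value and tests nothing relevant. This also stands. The Report would then print no parenteral end value at all.

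A third reply is that the p-value may belong to the mixed arm's fall or to the three-group test. That is possible, and several p-values on nearby outcomes do describe changes within arms. But a fall within one arm is not a comparison between arms, and a three-group result does not say which arms differ. Pooling the isolated arms is not among the prescribed pairs, and the enteral gap carries it.

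Nor can a Mann-Whitney result be excluded. On simulated normal data forced to the printed means and SDs, mixed against parenteral had a median p of 0.14 and fell below 0.03 in about 6% of datasets.

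**Conclusion.** The superiority claim over parenteral feeding is not supported by what is printed. As end-of-support means with SDs, the figures give -100 kcal/day (95% CI -229 to 29, p = 0.12) against parenteral and -250 (95% CI -385 to -116, p = 0.0006) against enteral. This rests on three things that the Report does not state: that ± is the SD, that the means are end values, and that levels rather than changes are compared.

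A reader might infer three stronger things. The first is that p<0.03 was miscalculated; steps 3 and 4 give several tests that could yield it. The second is that exactly half of the ranking fails; that holds only under the SD reading, since the enteral contrast fails as well if every ± is a standard error. The third is that 105.2 is a misprint; a variance ratio near 10 in a calculated quantity is a query for the source data, and skewed data or a different statistic could also explain it. The documents establish none of these. They also do not show that mixed and parenteral feeding are equivalent, since the interval is wide.

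**What to change.** In Results and discussion:

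- State which test gave p<0.03 and place the value beside the statement it tests. It need not be deleted.
- Label every ± as SD, standard error or CI half-width, and say whether each mean is initial or final.
- Check 105.2 against the source data.
- Report mixed minus enteral and mixed minus parenteral separately, as change from baseline or as baseline-adjusted end value, each with its 95% CI and p-value.

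Then reword that sentence and Conclusion item 3 so that an advantage over parenteral feeding is claimed only if its own contrast supports it.

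The cost is two contrasts re-run on data already held, a look-up of one value and a few reworded sentences. The headline for mixed feeding may become less favourable.

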This fact was obviously associated with the preservation/restoration of parietal digestion in the gastrointestinal tract in the early postoperative period, despite postoperative intestinal paresis of varying degrees, and the involvement of nutrients in anabolic processes with parallel “covering” of the required daily caloric intake by parenteral administration of mixtures.

Evaluation and subsequent analysis of the results of laboratory examination in groups of patients in a comparative aspect showed a relatively slow and gradual decrease in the level of total blood protein by the 5th day of the postoperative period, on average, by  $6.8 \pm 0.95\%$  of the initial values, which,

apparently, was due to increased catabolism and ongoing protein losses (exudation, drainage, etc.) with a fairly significant increase by the end of nutritional support.

Thus, a statistically significant increase in the level of total blood protein was noted in the mixed nutrition group ( $p = 0.004$ ). In the groups with enteral and parenteral nutrition, differences in the dynamics of total protein levels were found at the level of a statistical trend:  $p=0.108$  and  $p=0.129$ , respectively.

When analyzing changes in the number of blood lymphocytes, it should be noted that before the operation the relative value of lymphocytes in the groups was significantly reduced ( $25.9\pm3.7\%$ ), but taking into account the methods and volumes of the operation, the tension of the cellular and humoral parts of the immune system, the dynamics of their level was expressed in the form of a statistically significant increase in the level of lymphocytes in the postoperative period by 10-12 days.

Thus, there was a steady increase in the level of blood lymphocytes by the 10th day of the postoperative period in all groups, on average by 8.95% ( $p = 0.000$ ), by 10.35% ( $p = 0.003$ ), by 10.91% ( $p = 0.000$ ) respectively.

This dynamics reflects the positive effect on the immune status of patients of the combined use of parenteral and enteral types of nutritional support in the postoperative period in this group of patients.

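### Total protein: a p-value of 0.004 in the mixed arm beside 0.108 and 0.129 in the others, tied to no time pair and with no between-arm test, does not show that mixed feeding raised protein more

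*Combined protocol and SAP*

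**What the plan says.** The total-protein result is in the results text of the report, under Methods of statistical data analysis. It describes a gradual "decrease in the level of total blood protein by the 5th day of the postoperative period, on average", of 6.8 ± 0.95% of initial values, "with a fairly significant increase by the end of nutritional support". The fall is averaged over the groups; no arm-specific figure is given. The next sentence, worded as following from this, states that "a statistically significant increase in the level of total blood protein was noted in the mixed nutrition group" (p=0.004). For enteral and parenteral feeding, "differences in the dynamics of total protein levels were found at the level of a statistical trend", with p=0.108 and p=0.129.

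The methods text of the same section plans two kinds of comparison that bear on this. For repeated measurements it gives a Kendall test and then Wilcoxon tests "for each of the 3 pairs (baseline, after 5 days and after 10 days". For groups it gives an overall test and then tests "for each of the 3 pairs (groups 1 and 2, groups 1 and 3, groups 2 and 3".

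Conclusion item 2 says that total protein stayed more or less constant in all patients (100%) throughout nutritional support.

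**The concern.** The stated purpose, in both the protocol and the report, is to compare three types of feeding, and objective 2 covers protein metabolism. For total protein the reader gets one p-value per arm. The mixed arm is singled out because its p-value is below 0.05 and the other two are not. A difference in significance is not a significant difference: the three values could come from similar mean changes with different scatter.

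The reference point is also open. A rise described after a fall by day 5 may be counted from the day-5 low or from the preoperative value. Some recovery after surgical loss could occur under any feeding regimen. A change counted from the low also mixes depth of fall with recovery, so an arm that fell further has more to regain.

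At stake is whether the report has any evidence on how the arms compare for this outcome. The text also describes as a trend two results that are far from conventional significance and whose direction is not stated.

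**Working it through.** **The printed figure.** p=0.004 cannot be reproduced. The visible text gives no total-protein means, standard deviations, size of change, time pair or named test.

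**Which comparison could p=0.004 be?** Three readings fit the text.

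1. Day 5 to day 10, by Wilcoxon: recovery from the low.
2. Baseline to day 10, by Wilcoxon: net change from the preoperative level.
3. The overall Kendall test across the three times: evidence that the level varied, with no particular rise measured.

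The methods name these tests for rank or non-normal data and name no paired test for normal data, so even the type of test is inferred. Nor does the phrase about the end of support fix the day. The basal-metabolism results have "by the end of these types of energy subsidies (days 10-15"), while Conclusion item 3 has "by the end of nutritional support (days 15-20") and item 1 has days 12 to 15. Other outcomes do not settle the reference point either: mixed-arm transaminases at day 10 are referred to the day-5 value, and parenteral bilirubin to the preoperative value.

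**What do the p-values imply between arms?** Assume each is a two-sided within-arm p-value for one mean change, and use a normal approximation.

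- Mixed: p=0.004, z=2.878.
- Enteral: p=0.108, z=1.607.
- Parenteral: p=0.129, z=1.518.

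Let r be the standard error of the other arm's change divided by that of the mixed arm. If every arm rose, the contrast is z = (z_mixed − r × z_other) / √(1 + r²).

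With equal standard errors (r=1):

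- Mixed v enteral: (2.878 − 1.607)/√2 = 0.90, p≈0.37.
- Mixed v parenteral: (2.878 − 1.518)/√2 = 0.96, p≈0.34.

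Over an assumed range of r:

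| r | Mixed v enteral, p | Mixed v parenteral, p |
|---|---|---|
| 0.5 | 0.064 | 0.058 |
| 0.75 | 0.181 | 0.164 |
| 1 | 0.369 | 0.336 |
| 1.5 | 0.795 | 0.739 |
| 2 | 0.880 | 0.944 |

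The report does not state the direction of change behind p=0.108 and p=0.129. If both were net falls, the signs reverse. With r=1:

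- Mixed v enteral: (2.878 + 1.607)/√2 = 3.17, p≈0.002.
- Mixed v parenteral: (2.878 + 1.518)/√2 = 3.11, p≈0.002.

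The same printed p-values therefore fit anything from no difference to a clear one.

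**Agreement with the conclusions.** A pooled mean fall of 6.8% by day 5, followed by a significant rise in one arm, does not sit with a level described as roughly constant in 100% of patients.

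**The case against.** The methods do name fixed days (baseline, day 5, day 10) and do plan pairwise group tests. The fault is therefore in tying the result to the plan and in reporting it, not in a lack of planned time points. That is right, and the point is limited to it.

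A reader might go further and infer that p=0.004 is only a rebound and that mixed-arm patients ended below their preoperative level. The documents do not support that. A net rise from baseline, or an overall Kendall p-value, fits the wording equally well. The 6.8% fall is pooled over groups, ±0.95 is not labelled as a standard deviation or a standard error, and no standard deviation for any later change is given. Any calculated end level would rest on assumptions, so none is offered here.

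A reader might also take 0.37 and 0.34 as showing that the arms did not differ. They hold only for equal standard errors and increases in every arm, and the table and the reversed-sign case show how far they move.

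It is also fair to say that the Conclusion claims no mixed-feeding benefit on total protein; its superiority claims rest on the NRI and SGA scales and on basal metabolism. This limits the consequence, but the results text still singles out the mixed arm and conflicts with Conclusion item 2. Finally, a figure is missing from the text available for review and may hold protein values, so statements about absent figures apply to the visible text only.

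**Conclusion.** The concern holds in this form: the reported p-values do not show that mixed feeding raised total protein more than enteral or parenteral feeding. That conclusion does not depend on which time pair was used. It rests on reading one p-value per arm as within-arm testing, which is inferred because no test is named.

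The comparison is undetermined as reported. The implied between-arm p is about 0.37 and 0.34 if all arms rose with equal standard errors, 0.06 to 0.94 over standard-error ratios of 0.5 to 2, and about 0.002 if the other arms fell and standard errors were equal. Whether p=0.004 reflects recovery from day 5 or a gain over the preoperative level is also open. The conflict with Conclusion item 2 stands on the text alone. This should be corrected, but it does not undermine the report's main superiority claims, which rest on other outcomes.

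**What to change.** - Use the change from the preoperative value to day 10 as the contrast for total protein. Both times are already in the methods. Say that this contrast was fixed after the data were collected.
- Compare arms on that change with preoperative total protein as covariate. Report the mixed-minus-enteral and mixed-minus-parenteral differences with 95% confidence intervals.
- Give each arm's day-10 mean relative to its preoperative mean, so that the reader can see whether it ended above or below.
- Report the day 5 to day 10 change only as recovery.
- Delete the description of p=0.108 and p=0.129 as a statistical trend.
- Reconcile the total-protein results with Conclusion item 2.

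The cost is a small reanalysis of data already collected. The mixed-arm claim may weaken as a result.

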**Scientific consultants:**

Ph.D., associate professor, [name]

[contact]

e-mail: [contact].

Doctor of Medical Sciences, [name] [name]

**Foreign consultant:** MD, PhD, professor [name] (Poland)

**Name and address of the organization where the research is being conducted:** Karaganda State Medical University, department of resuscitation, anesthesiology and emergency medicine. Karaganda, [name] and KGP OOD [name].

**Name and address of the laboratory involved:** Research Center Laboratory of the Karaganda State Medical University, Karaganda, [name]

**Brief Summary:** A pressing concern involves the efficient and intensive treatment of complications arising from malignant tumors in the hepatopancreatoduodenal region. This matter is closely tied to rectifying energy deficits, addressing insufficient body weight, and restoring proper metabolic processes. This is particularly crucial post-surgery, as the process is hindered by significant hypercatabolism, heightened nutritional requirements, and the presence of intoxication syndrome.

**Methods.** An investigation was carried out on 91 individuals aged 18 years and older who were afflicted with malignant tumors situated in the hepatopancreatoduodenal area. These patients were categorized into three distinct groups, each receiving a different form of nutritional assistance.

The assessment encompassed various aspects of the patients' nutritional well-being, including outcomes from the screening protocol, body mass index, basal metabolic rate, and critical laboratory measurements such as blood lymphocyte count, total protein level, total bilirubin concentration, as well as ALaT and ASaT levels.

**Keywords:** nutritional status, nutritional deficiency, nutritional support, sips, oncology, nutrition, tumors of the hepatopancreatobiliary zone.

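### The report credits the lymphocyte rise to combined parenteral and enteral feeding, but lymphocytes rose by similar amounts in all three arms and no between-arm result is given

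*Combined protocol and SAP*

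**What the plan says.** The groups are set out under Research objectives in the report: "The first group (n=31) included patients who received enteral nutrition (EN) after surgery"; "The second group (n=30) included patients receiving parenteral nutrition (PN"); and a third group of 30 on mixed nutrition. All three received some form of nutritional support.

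Under Results and discussion, the lymphocyte paragraph opens with "When analyzing changes in the number of blood lymphocytes". It gives one level: "before the operation the relative value of lymphocytes in the groups was significantly reduced", at 25.9±3.7%. It then reports that "there was a steady increase in the level of blood lymphocytes by the 10th day of the postoperative period in all groups", by 8.95% (p = 0.000), 10.35% (p = 0.003) and 10.91% (p = 0.000) respectively. The next sentence interprets this: "This dynamics reflects the positive effect on the immune status of patients of the combined use of parenteral and enteral types of nutritional support".

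The section on methods of statistical data analysis describes three-group tests followed by tests on each of the three pairs of groups. No such result is given for lymphocytes.

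The Brief Summary of the protocol lists the marker among "critical laboratory measurements such as blood lymphocyte count".

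**The concern.** The sentence draws a comparative, causal conclusion from three within-arm changes. A rise from baseline in one arm says nothing about whether that arm did better than another, and here all three arms rose. Enteral feeding alone and parenteral feeding alone show nearly the same change as the mixed regimen, so the pattern does not point to combined use.

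The study's stated purpose is to compare the three feeding types. A statement that one type improved immune status, without a between-arm estimate, answers that question without the evidence it needs. It also lends apparent support to the report's overall preference for mixed feeding.

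A second, smaller difficulty is that the unit of the rises is unclear, so a reader cannot tell how large the change is.

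**Working it through.** **Inputs (report, Research objectives and Results and discussion).** Enteral (EN): n = 31, rise 8.95, p = 0.000. Parenteral (PN): n = 30, rise 10.35, p = 0.003. Mixed (MN): n = 30, rise 10.91, p = 0.000. I read p = 0.000 as below 0.0005. Matching figures to arms assumes that the results follow the order of the group list. That order puts the largest rise in the mixed arm. If the third figure were not the mixed arm's, a single-route arm would have risen most.

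**Can the stated figures be reproduced?** No. The report gives no day-10 means, no standard deviations of change and no patient data.

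**Contrasts the attribution would need, in the stated units.**
- MN − PN = 10.91 − 10.35 = 0.56
- MN − EN = 10.91 − 8.95 = 1.96
- Single-route arms pooled: (31 × 8.95 + 30 × 10.35)/61 = 9.64, so MN − pooled = 1.27

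**Rough precision.** Suppose each p-value comes from a two-sided paired t-test. Then SE = rise / t(1 − p/2, n − 1).
- PN: 10.35/3.239 = 3.20. Allowing for rounding of p (0.0025 to 0.0035), the SE lies between 3.13 and 3.26.
- MN − PN: the SE of the difference cannot be below the PN SE. So |t| is at most 0.56/3.13 = 0.18 and p is at least about 0.86, whatever the MN SE.
- With p = 0.000 set at 0.0005, the SEs at their upper limits are EN 8.95/3.902 = 2.29 and MN 10.91/3.918 = 2.78.
- MN − PN: SE = √(2.78² + 3.20²) = 4.24; 95% CI 0.56 ± 1.96 × 4.24, or −7.7 to 8.9.
- MN − EN: SE = √(2.78² + 2.29²) = 3.61; 95% CI 1.96 ± 1.96 × 3.61, or −5.1 to 9.0; p about 0.59.

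MN − EN is not bounded as firmly, because p = 0.000 gives only an upper limit on each SE. For 1.96 to reach p of about 0.04, the SD of change in both arms would have to be about 3.7 in the units of the rises. The parenteral result implies 3.20 × √30 = 17.5.

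**What the rises could mean.** Using the one pooled preoperative value, 25.9%, for every arm:

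| Reading | EN | PN | MN | MN − PN | MN − EN |
|---|---|---|---|---|---|
| Percentage points: day-10 level | 34.85% | 36.25% | 36.81% | 0.56 points | 1.96 points |
| Relative change in the percentage: day-10 level | 28.2% | 28.6% | 28.7% | 0.15 points | 0.51 points |
| Change in the absolute count | not derivable | not derivable | not derivable | – | – |

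In the second row the differences are 25.9 × 0.56/100 and 25.9 × 1.96/100. The report does not say which reading applies.

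**The case against.** **The sentence may not be about the mixed arm.** The report usually calls the third arm mixed. Here it speaks of combined use, directly after describing all groups, and the text appears to be a translation. It may mean that nutritional support by both routes helped. That ambiguity stands, but the looser reading is unsupported too: every arm was fed, so a within-arm rise cannot be told apart from recovery after surgery.

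**The back-calculation assumes paired t-tests.** For related, non-normal or rank data the methods specify the Kendall and then the Wilcoxon test, from which an SE cannot be recovered in this way. This stands, so the intervals are illustrative only. The point does not depend on them: the three rises and the missing between-arm result are enough.

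**The stakes are limited.** This also stands. The three items of the Conclusion concern nutritional scales, total protein and basal metabolism. The objectives and hypothesis name no immune outcome.

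**A stronger reading that a reader might infer** is that the rise is an artefact of the white-cell differential, with the lymphocyte percentage rising because other white cells fell. The documents do not establish this. Only the preoperative value is called relative; the text also speaks of number and level. Starting from the preoperative 25.9% with an unchanged lymphocyte count, total white cells on day 10 would have to be about 8–10% below the preoperative level (1 − 25.9/28.2 to 1 − 25.9/28.7) or 26–30% below it (1 − 25.9/34.85 to 1 − 25.9/36.81). Resolution of a surgical white-cell response would not by itself produce that, and no white-cell counts are reported.

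A reader might also take lymphocytes to be the measure of the immunological state planned in the protocol's Methods and procedures. The protocol lists that item separately and does not say how it is measured.

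**Conclusion.** The attribution is unsupported as written. Lymphocytes rose in all three arms, the mixed arm leads by only 0.56 and 1.96 of the stated units (assuming the listed group order), and no between-arm lymphocyte result is reported although pairwise tests are described. Under the paired-t assumption, the difference between mixed and parenteral feeding is far from significant; the difference from enteral feeding is less tightly bounded.

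The correct statement is that no between-arm difference was shown. It would go too far to say that the feeding types are equivalent, because the illustrative intervals run from about −8 to +9.

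The unit of the rises is a secondary reporting gap. It is not evidence that the rise is spurious.

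Severity is moderate: the sentence misstates a comparative finding, but no item in the Conclusion relies on it.

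**What to change.** 1. Delete the sentence crediting combined feeding. State that lymphocytes rose by day 10 in all three arms and that no between-arm difference was shown. This needs no new data.
2. Report the three between-arm differences in change from baseline to day 10 with 95% confidence intervals, adjusted for the baseline lymphocyte value, and base any claim about feeding type on these alone. Adjustment is advisable because the arms differed before surgery: normal status on the SGA scale was recorded in 24 of 31 enteral, 19 of 30 parenteral and 17 of 30 mixed patients. The cost is one small analysis of the existing data on 91 patients.
3. State whether the rises are percentage points, relative change in the percentage, or change in the count. If total white-cell counts were recorded, tabulate absolute lymphocyte counts by arm and visit and use them in step 2. None of the laboratory lists names a total white-cell count, so this may not be possible. If it is not, report the marker as a percentage and say so.

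The report loses a claim of immune benefit for one feeding type. The Conclusion needs no change on this account.
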